5.5 Participant Discontinuation

In order to ensure safety, female participants who become pregnant during the study will be required to discontinue participation in the intervention. Participants may be asked to stop study intervention if any situation arises that, in the investigator’s judgment, poses a safety risk.

Participants who must stop the study intervention will still be asked to complete assessment visits as scheduled.

5.6 Participant Remuneration

Participants will be paid up to a total of \$40 for their participation in the trial to compensate for their time, travel arrangements, and the burden of participation. Participants will be paid \$20 for attending the each of the assessment visits (baseline and Week 8). Participants will be paid for each eligible visit using the UT Southwestern Greenphire ClinCard system. Participants will also receive instructions on how use the card.

6.0 STUDY ASSESSMENTS

6.1 Schedule of Assessments

Study assessments may have a window of +/- 2 weeks to allow visits to occur concurrent with standard of care visits. Week 8 and 10 can occur at the same visit if needed.

Remote phone/video visits are allowed

Assessment	Baseline	Week 8	Week10
Informed Consent	X		
Demographics (age, gender, race, diagnosis, stage)	X		
Weight, height, ECOG performance status	X		
Physical Activity Vital Sign	X		
Physical Activity Readiness Questionnaire	X		
Eligibility Criteria	X		
Completion of Fitbit Versa Registration	X		
Physical Activity Stages of Change Questionnaire	X	X	
Physical Activity Self-Efficacy Questionnaire	X	X	
Multidimensional Outcome Expectation for Exercise Scale	X	X	
Affective Associations	X	X	
Affective Attitudes	X	X	
Anticipated Affect	X	X	
Functional Assessment of Cancer Therapy - Kidney Symptom Index*	X	X	
Functional Assessment of Cancer Therapy - Gastric Cancer~	X	X	
Quick Inventory of Depressive Symptomatology	X	X	
Brief Fatigue Inventory	X	X	
Generalized Anxiety Disorder	X	X	
Pittsburgh Sleep Quality Index	X	X	
Pain - Frequency, Intensity, and Burden Scale	X	X	
Dimensional Anhedonia Rating Scale	X	X	
Exercise Vital Sign	X	X	
Intervention Acceptability			X

* Only applicable for renal cell carcinoma patients

~ Only applicable for any GI cancer patient

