5.4 Treatment and Study Intervention

Participants will receive a Fitbit Versa and instructions on its use. Participants will be asked to wear the device for eight weeks, removing it only for charging and when engaging in activities in which the device could be submerged in water beyond its recommended depths (water resistant up to 50 meters).

Manual Connection and Pre-Authorization: At baseline, a research staff member will create a unique email and password combination in order to create an account on Fitbit.com.

During the account creation process the following information will be entered:

- First Name: A de-identified placeholder name will be entered
- Last Name: A de-identified placeholder name will be entered
- Date of Birth: The first day of the month of birth will be entered OR The first day of the year of birth will be entered.
- Gender/Sex: The participant's gender will be entered.
- Height: The participant's height will be entered.
- Weight: The participant's weight will be entered.

It is important to note that the personal demographic details - date of birth, gender, height, and weight - are required for accurate estimation of data captured by the Fitbit Device.

The Fitbit account will be connected to a research device. Once the device is connected to the study-generated and study-controlled Fitbit account it will be manually connected to the Fitabase platform and assigned a unique study ID so that data will be synced and available for viewing and downloading by research staff. All data associated with the Fitbit device will be linked to the chosen unique study ID in the Fitabase platform.

Participants will be given the connected Fitbit device and be provided with the associated email/password so that they may login into the Fitbit.com user account, use the online dashboard, and associated mobile applications. They will be informed that research staff will be able to access, view, and download their data through the Fitabase platform. The participant will be given a copy of the Fitabase Terms of Use and the Privacy Policy for review during the consent process. By consenting to use the Fitbit device as part of this study the participants also signals an acceptance of the Fitabase Terms of Use and Privacy Policy.

At enrollment, participants will indicate a preferred time to receive affective framing messages and EMA prompts (morning), and intention planning prompts (evenings).

Ecological momentary assessment.

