Each morning during the eight-week intervention, participants will receive questions about their current affect, intent to engage in physical activity, and self-efficacy for engaging in physical activity. At each request, participants will be given the option to “snooze” the request for up to one hour. The assessment questions will be viewed and responded to on the Fitbit Versa device. We will utilize the Fitbase Engage platform (see Figure 3), which utilizes the Fitbit SDK to deliver assessments and message prompts via the Fitbit Versa. Assessment questions have been validated for their use in EMA.⁵⁻⁷ Daily questions will include:

Figure 3. Representations of messages delivered via the Fitbase Engage platform.

*Actual messages will be customized as described below.

Physical Activity Intention (One item; 1 strongly disagree to 5 strongly agree)

“I intend to meet my goal of XXX steps today”

Physical Activity Self-Efficacy (One item; 1 not confident at all to 5 completely confident)

“I believe I can complete my goal of XXX steps today.”

Affect (Nine items assessing positive and negative affect; 1 not at all to 5 extremely)

“How (happy, cheerful, relaxed, stressed, anxious, angry, depressed, energetic, fatigued/tired) do you feel right now?”

Affective Framing Messages. After completing the daily EMAs, participants may receive an affective framing message. Message delivery will occur on a 1:1 randomization schedule, such that participants will receive messages on 28 of the 56 intervention days. The study biostatistician will generate randomization schedules for each participant using block randomization with variable block sizes. Messages will be randomly selected from a pool of 14 messages, meaning each message will be received twice during the eight-week study. Messages will emphasize potential improvements in mood, energy, and calmness.^{8,9} Examples of these messages:

“Research has shown that physical activity often results in improved mood.”

“Most people report feeling happier and more relaxed after exercise.”

Weekly Goal Setting. Each Sunday evening, participants will receive a prompt to select a step goal for the upcoming week. Along with this prompt, participants will receive feedback on their activity during the previous week. Participants will receive either: 1) the average daily number of steps taken during the previous week, or 2) the highest daily number of steps taken during the previous week.

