6.1.1 Study Assessments

At baseline and at the end of the eight-week intervention, participants will complete assessments of: 1) potential moderators of physical activity behavior change, and 2) psychosocial outcomes.

Primary outcome measurement:

Fitbit Versa. The primary outcome measure will be daily step counts measured by the Fitbit Versa. Wrist-worn Fitbit devices demonstrate acceptable reliability and validity for measuring step counts.¹³ We will utilize Fitabase, a comprehensive data management platform that utilizes the Fitbit partner-level API, to capture near real-time participant activity data.

Theoretical moderators of physical activity behavior change:

Physical Activity Stages of Change Questionnaire: 4-item scale that assesses current stage of activity.

Physical Activity Self-Efficacy Questionnaire: 3-item scale that assesses self-efficacy for physical activity.

Multidimensional Outcome Expectations for Exercise Scale: 15-item scale that assesses a multitude expectations for physical activity.

Affective associations: 6-item scale that assesses feelings about exercise.

Affective attitudes: 3-item scale that assesses feelings during exercise.

Anticipated affect: 2-item scale that assesses the anticipated affect of regular physical activity.

Psychosocial Outcomes:

Functional Assessment of Cancer Therapy: 19-item scale that assesses quality of life in cancer patients.

Quick Inventory of Depressive Symptomatology – Self-Rated (QIDS-SR): 16-item scale that assesses severity of depression-specific symptoms.

Brief Fatigue Inventory (BFI): 9-item scale that assesses fatigue in cancer patients

Generalized Anxiety Disorder 7 item Scale (GAD-7): 7-item scale that assesses anxiety symptoms.

Pittsburgh Sleep Quality Index (PSQI): 19-item scale that assesses sleep quality and disturbances.

Pain – Frequency, Intensity, and Burden Scale (P-FIBS): 4-item scale that assesses the frequency, intensity, and burden of pain.

Dimensional Anhedonia Rating Scale (DARS): 21-item scale that assesses anhedonia.

Exercise Vital Sign (EVS): 2-item scale that assesses an estimate of an individual's physical activity.

Intervention Acceptability:

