After completion of the study, at Week 10, participants will complete an intervention acceptability questionnaire. Using a series of 5-point Likert scale questions, we will evaluate overall intervention satisfaction and also satisfaction with specific components of the intervention (i.e., message content, message frequency, Fitbit ease of use, etc.)

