7.0 STATISTICAL ANALYSES

Aim 1. Aim 1 of the proposed pilot study will evaluate the feasibility and acceptability of the proposed intervention. The feasibility of the study will be assessed by the following criteria displayed in Table 1.

Table 1. Feasibility and acceptability measures and benchmarks.

FEASIBILITY		
	Measure	Benchmark
Recruitment	Enrollment rate	7 participants/month
Intervention Adherence	Response rate to intervention messages Response rate to EMA prompts Fitbit use (% of days with > 8 hours wear time)	75% 75% 70%
Retention	Completion of follow-up assessments	90%
ACCEPTABILITY		
	Measure	Benchmark
Intervention satisfaction	Satisfaction questionnaire	75% of participants rate ≥ 4 on 5-point Likert scale

Aim 2.

Hypothesis 2a: *Participants will have greater daily step counts on days receiving an affective framing message compared to non-message days.*

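### The two-sided 2-week visit window lets the end-of-intervention questionnaires be completed from day 42, with the last quarter of the intervention still to be delivered

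*Combined protocol and SAP*

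**What the plan says.** Section 6.1 (Schedule of Assessments) sets one window for all visits: "Study assessments may have a window of +/- 2 weeks to allow visits to occur concurrent with standard of care visits". It then adds: "Week 8 and 10 can occur at the same visit if needed". It also permits remote visits by phone or video. Neither sentence ties the Week 8 visit, or a combined visit, to the last day of the intervention.

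Section 6.1.1 gives the intended timing of the moderator and psychosocial questionnaires: "At baseline and at the end of the eight-week intervention, participants will complete assessments of" these two groups of measures. For acceptability it says: "After completion of the study, at Week 10, participants will complete an intervention acceptability questionnaire".

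Section 5.4 fixes the length of the intervention. On the device: "Participants will be asked to wear the device for eight weeks". For affective framing messages, and again for planning prompts: "participants will receive messages on 28 of the 56 intervention days".

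Section 7.0 sets the Aim 1 benchmarks. Retention is judged on completion of follow-up assessments (90%). Acceptability is met if "75% of participants rate ≥ 4 on 5-point Likert scale".

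**The concern.** A post-intervention measure should be taken once the intervention has been delivered. The window in section 6.1 is symmetric, so a site that matches the Week 8 assessment to a clinic visit at week 6 follows the protocol while messages and daily assessments still have two weeks to run. Because the stated purpose of the window is alignment with standard-of-care visits, early visits are an expected use of it.

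Three things are at stake.

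- **Psychosocial and moderator questionnaires.** Week 8 is their only post-baseline measurement. Under the rule as written, these scores can mix states during, at the end of and after the intervention. Their timing would follow each patient's clinic schedule, which may in turn follow cancer treatment.
- **Retention.** A participant assessed on day 42 has met the Week 8 part of the retention measure even if they disengage during the last two weeks.
- **Acceptability.** The questionnaire covers, among other things, satisfaction with message frequency. If it could be completed at an early combined visit, the rater would not yet have had the full course being rated. Section 1.0 makes acceptability one of the two grounds for choosing which components enter the later adaptive intervention.

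**Working it through.** **Inputs.** Intervention length of eight weeks, and 28 message days per component (section 5.4). Window of 2 weeks either side, and permission to combine Weeks 8 and 10 (section 6.1). Intended timing of the questionnaires (section 6.1.1). Visit weeks and intervention days are assumed to be counted from the same start.

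**The plan's own figure.** 8 weeks × 7 = 56 days, and 56 × 0.5 = 28 message days per component. Both match section 5.4.

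**Windows implied by section 6.1.**

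| Visit | Earliest | Latest |
|---|---|---|
| Week 8 | 8 − 2 = week 6 (day 42) | 8 + 2 = week 10 (day 70) |
| Week 10 | 10 − 2 = week 8 (day 56) | 10 + 2 = week 12 (day 84) |
| Both windows respected | week 8 (day 56) | week 10 (day 70) |

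**Delivery at the earliest Week 8 visit.**

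- Delivered: 42/56 = 75%, or about 42 × 0.5 = 21 of 28 message days per component.
- Remaining: 56 − 42 = 14 days, and 14/56 = 25%.
- Still to come: about 14 × 0.5 = 7 framing messages, about 7 planning prompts, and 14 morning assessments.

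The Week 8 questionnaires can therefore fall anywhere from 14 days before to 14 days after the intervention ends (day 42 to day 70), with between 42 and 56 days of intervention received.

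**The combined visit.** If both windows apply, it falls in weeks 8 to 10 and cannot precede the end of the intervention. A combined visit at week 6 would be 10 − 6 = 4 weeks before nominal Week 10, and 8 − 6 = 2 weeks outside that visit's own window. It is possible only if the same-visit sentence overrides the Week 10 window. The document does not say whether it does.

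**What does not depend on visit dates.** The primary outcome is the daily step count, collected by the device. The models for Hypotheses 2a to 2c in section 7.0 use daily steps, daily assessments for 2a and 2b, and baseline values of the questionnaires. None uses a Week 8 questionnaire score.

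**After the change.** With a Week 8 window of 0 to +2 weeks, the earliest visit is at day 56, so 56/56 = 100% of intervention days are covered. A combined visit then falls in weeks 8 to 10, inside both windows.

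**The case against.** The strongest reply is that little of the trial's main analysis rests on visit dates. This stands: step counts, Hypotheses 2a to 2c and their power are untouched, and section 7.0 specifies no analysis of the Week 8 questionnaire scores. The window also has a practical reason, since it spares patients with cancer additional visits. That justifies a window, but not one that opens before the intervention has ended.

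A reader might infer that the plan clearly permits acceptability to be rated at week 6. The documents do not support that. Section 6.1.1 places the questionnaire after completion, and the Week 10 window opens at week 8. The same-visit sentence can be read as only removing the need for two separate visits. It is silent on an earliest date, so this is an ambiguity to settle, not a permission. The overlap of the two windows is not a fault either, because it is what makes a valid combined visit possible.

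A reader might also treat the acceptability benchmark as a stop/go rule, or suppose that a separate Week 10 visit would lose dissatisfied participants. Section 7.0 calls the figures benchmarks and attaches no stopping rule to them, and nothing in the documents shows selective loss at Week 10.

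The objection does not remove the central point. No sentence elsewhere stops a Week 8 visit on day 42, and that conflicts with section 6.1.1.

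**Conclusion.** The point holds in a limited form. Section 6.1 makes a Week 8 visit compliant from day 42, when 75% of the intervention has been delivered and 25% (14 of 56 days) is still to come. Section 6.1.1 asks for these measures at the end of the intervention. The affected items are the only post-baseline psychosocial and moderator measures and the Week 8 part of the retention benchmark. The acceptability benchmark is affected only if the same-visit sentence is read as overriding the Week 10 window.

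The counts of 7 messages and 7 prompts are averages under 1:1 randomization, and the day counts assume that visits and intervention days share one starting point. The documents do not show how many visits would fall early, so 14 days is the limit the rule allows, not an expected shift. The change is worth making because the rule itself allows mistimed measures and the correction is small.

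**What to change.** Amend section 6.1 in three respects:

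1. Make the Week 8 window 0 to +2 weeks (day 56 to day 70).
2. State that no Week 8 visit, and no combined Week 8 and Week 10 visit, may precede the last intervention day. This brings section 6.1 into line with both timing statements in section 6.1.1.
3. Record the actual date of each assessment, so that the time since the end of the intervention can be reported.

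The acceptability questionnaire can stay at Week 10, with the option to combine visits kept.

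The cost is a wording amendment and a narrower window, so fewer standard-of-care visits will coincide with Week 8. The phone and video visits already allowed by section 6.1 offset this.

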6.1.1 Study Assessments

At baseline and at the end of the eight-week intervention, participants will complete assessments of: 1) potential moderators of physical activity behavior change, and 2) psychosocial outcomes.

Primary outcome measurement:

Fitbit Versa. The primary outcome measure will be daily step counts measured by the Fitbit Versa. Wrist-worn Fitbit devices demonstrate acceptable reliability and validity for measuring step counts.¹³ We will utilize Fitabase, a comprehensive data management platform that utilizes the Fitbit partner-level API, to capture near real-time participant activity data.

Theoretical moderators of physical activity behavior change:

Physical Activity Stages of Change Questionnaire: 4-item scale that assesses current stage of activity.

Physical Activity Self-Efficacy Questionnaire: 3-item scale that assesses self-efficacy for physical activity.

Multidimensional Outcome Expectations for Exercise Scale: 15-item scale that assesses a multitude expectations for physical activity.

Affective associations: 6-item scale that assesses feelings about exercise.

Affective attitudes: 3-item scale that assesses feelings during exercise.

Anticipated affect: 2-item scale that assesses the anticipated affect of regular physical activity.

Psychosocial Outcomes:

Functional Assessment of Cancer Therapy: 19-item scale that assesses quality of life in cancer patients.

Quick Inventory of Depressive Symptomatology – Self-Rated (QIDS-SR): 16-item scale that assesses severity of depression-specific symptoms.

Brief Fatigue Inventory (BFI): 9-item scale that assesses fatigue in cancer patients

Generalized Anxiety Disorder 7 item Scale (GAD-7): 7-item scale that assesses anxiety symptoms.

Pittsburgh Sleep Quality Index (PSQI): 19-item scale that assesses sleep quality and disturbances.

Pain – Frequency, Intensity, and Burden Scale (P-FIBS): 4-item scale that assesses the frequency, intensity, and burden of pain.

Dimensional Anhedonia Rating Scale (DARS): 21-item scale that assesses anhedonia.

Exercise Vital Sign (EVS): 2-item scale that assesses an estimate of an individual's physical activity.

Intervention Acceptability:

After completion of the study, at Week 10, participants will complete an intervention acceptability questionnaire. Using a series of 5-point Likert scale questions, we will evaluate overall intervention satisfaction and also satisfaction with specific components of the intervention (i.e., message content, message frequency, Fitbit ease of use, etc.)

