A repeated-measures mixed effects model will be used as described in Klasnja et al. (2015) with participant and time as random effects and other effects as fixed. Daily step count will be the dependent variable while main effects of affective framing intervention (message/no message) and linear time effects will be within-subjects factors, and an intervention by time interaction term will be included. We also will consider more complex effects of time (e.g., quadratic effects). We will include scores of the Physical Activity Intention, Physical Activity Self-Efficacy, and Affect as time-varying covariates. As described in Klasnja, et al. (2015) we will include the scores for the day prior to the intervention so the covariates will not be affected by the intervention. We will also classify each day as a cancer treatment day (i.e. day on which chemotherapy or radiation therapy is received) or not and presence/absence of cancer treatment will also be a time-varying covariate. A time lag is not needed for this covariate as the timing of cancer treatment will not be influenced by the intervention. Presence/absence of an implementation planning message on each day will also be included as a time-varying covariate and an affective framing by planning message interaction will be included to assess synergistic effects of the two messages. The baseline measurement of theoretical moderators of physical activity behavior change (Physical Activity Stage of Change, Physical Activity Self-Efficacy, Multidimensional Outcome Expectations for Exercise Scale) and psychosocial characteristics Functional Assessment of Cancer Therapy – General, Quick Inventory of Depressive Symptomatology – Self-Rated, Brief Fatigue Inventory) will be considered as covariates as will other baseline demographic and clinical variables determined to improve the fit of the final model.

Hypothesis 2b: *Participants will have greater daily step counts on days receiving the implementation planning message compared to non-message days.*

The same repeated-measures mixed effects model described for Hypothesis 2a will be used for this hypothesis. Only the interpretation of the results will be different as the presence/absence of the implementation message will be the main effect and the affective framing intervention will be considered the covariate.

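### Precision only: the whole-day step outcome for Hypothesis 2a counts steps taken before the morning message, and no model covariate accounts for them

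*Combined protocol and SAP*

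**What the plan says.** Section 6.1.1 sets the outcome: "The primary outcome measure will be daily step counts measured by the Fitbit Versa". Section 7.0 states Hypothesis 2a on the same scale: "Participants will have greater daily step counts on days receiving an affective framing message compared to non-message days". Daily step count is the dependent variable in the 2a model, and no post-message window is defined.

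On timing, section 5.4 has each participant choose a morning time at enrollment for the EMA and framing message. The message comes only after the assessment: "After completing the daily EMAs, participants may receive an affective framing message". The assessment itself can be delayed: "At each request, participants will be given the option to “snooze” the request for up to one hour".

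The 2a model in section 7.0 contains:
- message, time and their interaction;
- prior-day intention, self-efficacy and affect;
- cancer treatment day;
- the planning message and its interaction with the framing message;
- optional baseline variables.

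None of these is a step count from earlier the same day. Hypothesis 2b uses the same model and differs only in which coefficient is interpreted.

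On data capture, section 6.1.1 says that Fitabase will be used "to capture near real-time participant activity data".

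**The concern.** The outcome window opens at the start of the day, but the exposure comes later in the morning. Steps before the message are fixed when the message is or is not sent, so for 2a they only add day-to-day noise to the outcome. They are also a pre-exposure measurement that is probably available on most days, and it is part of the outcome itself. Section 7.0 already follows the principle that time-varying covariates should precede the intervention, which is why it lags the EMA scores by a day. Pre-message steps meet the same test for 2a but are not used.

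What is at stake is precision. The power section describes 0.109 as the effect that 50 participants can detect, about half of a small effect, so modest extra residual variance is worth removing if that is cheap. The participant random effect already absorbs stable differences between early and late walkers. Only a person's day-to-day variation in early steps matters here.

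**Working it through.** **1. Reproduce the plan's figure.** Inputs from the power section of 7.0: 56 days, randomization probability 0.5 per day, alpha 0.05, power 80%, standardized effect d constant over the study. I used the micro-randomized-trial calculation: a noncentral F with 1 and N − 1 − q degrees of freedom, where q is the number of nuisance terms, and

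noncentrality = N × 56 × 0.5 × 0.5 × d².

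For N = 50 and d = 0.109 this is 50 × 56 × 0.25 × 0.011881 = 8.32, and power is 0.807 (q = 1). All five rows of the 2a/2b column (17, 50, 60, 70, 100) reproduce exactly for q from 0 to 3.

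**2. Effect of adjusting for pre-prompt steps.** Let v be the share of within-person daily step variance that pre-prompt steps explain. The documents do not give v, so it is assumed. Adjustment multiplies residual variance by (1 − v) and leaves the raw step difference unchanged. Hence:
- detectable effect = 0.109 × √(1 − v);
- noncentrality at 0.109 = 8.32 / (1 − v).

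| Assumed v | Detectable effect | Noncentrality at 0.109 | Power at N = 50 | N for 80% power |
|---|---|---|---|---|
| 0 | 0.109 | 8.32 | 0.807 | 50 |
| 0.05 | 0.106 | 8.75 | 0.826 | 47 |
| 0.10 | 0.103 | 9.24 | 0.846 | 45 |
| 0.20 | 0.097 | 10.40 | 0.885 | 40 |

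**3. Check for bias.** A simulation of 50 participants over 56 days, 1,500 runs for each v, used a true effect of 0.109 and uncorrelated early and later steps. Unadjusted and adjusted estimates both averaged 0.108 to 0.109. The ratio of adjusted to unadjusted variance was 0.91 at v = 0.10 and 0.81 at v = 0.20, close to 1 − v.

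**4. When early and later steps are correlated.** Write the daily total as Y = E + L, with E the early and L the later steps. The share of variance that E explains is

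v = (Var E + Cov(E, L))² / (Var E × Var Y).

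- Uncorrelated: v = Var E / Var Y.
- Half offset, Cov = −0.5 Var E: v = 0.25 × Var E / Var Y. If Var E is 10% of Var Y, v is 2.5% and the detectable effect is 0.109 × √0.975 = 0.108.
- Full offset, Cov = −Var E: v = 0, no gain.
- Positive correlation: v is larger than in the uncorrelated case.

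Under full offset, Var L = Var Y − Var E + 2 Var E = Var Y + Var E. Steps after the prompt would then be a noisier outcome than the daily total. That favours adjusting the whole-day outcome over replacing it.

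**The case against.** The strongest reply is that nothing in the plan is wrong. Daily steps are the declared outcome and match the daily step goal shown to participants. Randomization protects the contrast, the sample-size table reproduces, and the power section claims no gain from covariates. All of that stands. This is an efficiency suggestion, not an error.

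The second reply is that the gain is assumed and could be nil. With a daily goal, a person who walks early may walk less later. This stands as a limit on size, and a no-gain case belongs in the range. Zero gain needs an exact offset, however, so the advice still points the same way.

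The third reply is that the covariate harms Hypothesis 2b. Section 5.4 sends the planning prompt in the evening and asks about the following day, so early-morning steps may be part of its effect. Putting them in the shared model would remove that part from the planning coefficient. This stands and shapes the fix.

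The fourth reply concerns data. Near real-time capture, and bout-triggered prompts about an hour after activity, imply within-day timing, but no export interval is stated. The device comes off for charging, and the feasibility benchmark is more than 8 hours' wear on only 70% of days, so a low early count may mean non-wear. Both points stand. A cut-off at the fixed prompt time also leaves steps during a snooze unadjusted. That is the price of a cut-off that does not depend on participant behaviour.

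**Conclusion.** The point holds as a low-cost improvement in precision. The 2a outcome includes steps that the day's message cannot change, and no covariate in section 7.0 accounts for them. Under the assumed shares of 0% to 20%, the effect detectable with 80% power lies between 0.109 and 0.097, and power at 0.109 between about 0.81 and 0.89. At 5% the gain is about 2 power points. The shares are assumptions, and offsetting between early and later steps would reduce them.

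Three stronger readings are not supported:
- **That the 2a estimate is biased.** Assignment is randomized and pre-message steps precede it.
- **That the sample size is wrong or the study falls below 80% power.** The stated figure reproduces. A shortfall (power 0.786, 0.764 or 0.715 at shares of 5%, 10% or 20%) appears only if 0.109 is standardized to post-message variance. The hypotheses are stated on daily counts, and no SD in steps is given.
- **That the daily outcome should be replaced.** It is the plan's declared target, and a post-prompt count is not always more precise.

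**What to change.** Keep daily steps as the primary outcome and pre-specify the following in section 7.0.

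1. Fit 2a as its own model. Add that day's steps from midnight to the participant's preferred morning prompt time, fixed at enrollment, as a time-varying covariate. Define it the same way on message and non-message days; do not use EMA completion time.
2. Flag days without device wear before the prompt with an indicator, and state the wear rule and the value assigned to the covariate on those days.
3. Fit 2b without this covariate. Do not read the planning coefficient of the 2a model as the 2b effect.
4. Report steps from the prompt time to midnight as a supportive 2a outcome.

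The cost is SAP wording, an intraday step export from Fitabase (interval to be confirmed), a wear check, and two models in place of one shared model. Recruitment, visits, devices and message schedules do not change. These choices should be written down before the data are examined, since a covariate or window added later could look selective.
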